1.3.2 Secondary Objectives

- To compare loco-regional recurrence-free survival between study arms. See Evaluation of Outcomes (Section 7) for recurrence definitions.
- To compare disease-free survival between study arms.
- To compare grade 3 or higher specific adverse event profiles between study arms; specific comparisons will include AEs at 1, 3, 6 and 12 months post therapy.
- To compare pulmonary function between patients treated with SBRT and patients treated with SR.
- To compare the adverse events and PFTs in each arm for patients with low or high Charlson comorbidity index scores, including a test interaction between Charlson comorbidity index scores (low vs. high) and treatment arm.

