2.1 Eligibility Criteria

- 1. Age \geq 18 years.
- 2. ECOG performance status (PS) 0, 1, or 2.
- 3. Biopsy-proven non-small cell lung cancer (NSCLC).
- 4. Tumor \leq 3 cm maximum diameter, clinical stage Ia or selected Ib (i.e., with visceral pleural involvement) by PET/CT scan of the chest and upper abdomen performed within 60 days prior to registration.
- All clinically suspicious mediastinal N1, N2, or N3 lymph nodes (> 1 cm short-axis dimension on CT scan and/or positive on PET scan) confirmed negative for involvement with NSCLC by one of the following methods: mediastinoscopy, anterior mediastinotomy, EUS/EBUS guided needle aspiration, CT-guided, video-assisted thoracoscopic or open lymph node biopsy.
- 6. Tumor verified by a thoracic surgeon to be in a location that will permit sublobar resection.
- 7. Tumor located **peripherally** within the lung. NOTE: Peripheral is defined as not touching any surface within 2 cm of the proximal bronchial tree in all directions. See the diagram in Section 2.2. Patients with non-peripheral (central) tumors are NOT eligible.
- 8. No evidence of distant metastases.
- 9. PFTs with DLCO within 90 days prior to registration.
- 10. Patient at high-risk for surgery by meeting a minimum of one major criteria or two minor criteria as described below:

Major Criteria

- FEV1 \leq 50% predicted
- DLCO \leq 50% predicted

Minor Criteria

- Age ≥ 75
- FEV1 51-60% predicted
- DLCO 51-60% predicted

- Pulmonary hypertension (defined as a pulmonary artery systolic pressure greater than 40mm Hg) as estimated by echocardiography or right heart catheterization
- Poor left ventricular function (defined as an ejection fraction of 40% or less)
- Resting or Exercise Arterial $pO2 \le 55 \text{ mm Hg or } SpO2 \le 88\%$
- pCO2 > 45 mm Hg
- Modified Medical Research Council (MMRC) Dyspnea Scale \geq 3.

Grade	Description
0	No breathlessness except with strenuous exercise
1	Breathlessness when hurrying on the level or walking up a slight hill
2	Walks slower than people of the same age on the level because of breathlessness or has to stop for breath when walking at own pace on the level
3	Stops for breath after walking about 100 yards or a few minutes on the level
4	Too breathless to leave the house or breathless when dressing or undressing

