2.2 Proximal Bronchial Tree Diagram (from RTOG 0236)

2.3 Staging Criteria

Patients will be staged according to the 7th edition of AJCC Cancer Staging Manual, 2010. See the staging reference in the Appendices.

3 Study Calendar

	Within 60	After	ARM	1 (SR)	ARM 2	(SBRT)				(From	B date o	OTH A f surge	RMS rv/end/	of SBR	T)			At time
days prior to reg. (except where noted)	reg. and before SBRT or surgery	At time of surgery	4 weeks post- op	Before final SBRT (same day)	4 weeks after SBRT	3 mo.	6 mo.	9 mo.	12 mo.	15 mo.	18 mo.	21 mo.	24 mo.	30 mo.	36 mo.	Yearly to 5 years	of disease relapse / PD	
Credentialing	x ¹																	
History & Physical, ECOG/Zubrod PS	Х			X		X	Х	Х	Х	Х	Х	Х	Х	Х	Х	Х	X	X
Pregnancy test	x ²																	
Tumor biopsy (and LN biopsy, if needed)	Х																	x ⁹
Pulmonary Function Tests	x ³						Х	Х		Х				Х				
PET/CT scan chest/upper abdomen	Х							Х		Х				Х		Х	Х	x ⁹
CT scan chest/upper abdomen				x ⁷			Х		Х		Х	Х	Х		Х			x ⁹
Adverse event assessment		X		Х		X	Х	Х	Х	Х								
Charlson Comorbidity Index		Х																
Blood specimen collection ⁴		x ⁵		X	X			Х		Х		Х		Х		Х	Х	
Tissue specimen collection ⁴			X															
EQ-5D, LCSS, LASA, UCSD SOB questionnaires		X		X		X	Х	X		X				Х				
QA submission to ITC		x ⁶		x ⁸		x ⁸												
Image submission to ITC																		x ⁹

1 Credentialing for surgery, brachytherapy, and SBRT may be completed any time prior to first registration. See Credentialing (Section 12).

2 For patients of childbearing potential.

3 Baseline PFTs are required within 90 days prior to registration. PFTs must include routine spirometry and DLCO. Arterial blood gases are not required but may be used as minor criteria for study enrollment. See Eligibility Criteria (Section 2.1).

4 Specimen collection is required for consenting patients only. See Biospecimen Collection (Section 13).

5 Pre-treatment blood specimen may be collected at the time of surgery for patients being treated on Arm 1.

6 Submission to ITC of the first patient's treatment plan is required prior to treatment for each type of SBRT system used at a site. See Quality Assurance Requirements (Section 5.4).

7 Post-implant CT scan is required for Arm 1 patients receiving brachytherapy.

8 See Quality Assurance Requirements (Section 5.4).

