Bronchial injury with subsequent focal collapse of lung may impair overall pulmonary status. It also makes further assessment of tumor response more difficult as the collapsed lung approximates the treated tumor. Because atelectatic lung and tumor have similar imaging characteristics, radiology reports will often describe the overall process as progressive disease while the actual tumor may be stable or shrinking. Investigators are referred to the strict criteria for progressive disease to avoid such mischaracterization.

The consequences of bronchial toxicity, e.g., cough, dyspnea, hypoxia, impairment of pulmonary function test parameters, pleural effusion or pleuritic pain (associated with collapse), will all be graded and reported on adverse event forms.

Chest Wall Pain and/or Fracture (Rib)

When treating lesions about the chest wall, some patients will experience chest wall pain either as a result of intercostal neuropathy or rib fracture. Focal radiation induced osteoporosis can result in both occult and obvious rib fractures generally propagated by severe coughing/sneezing episodes or chest wall trauma (e.g., bumping into a kitchen cabinet). The pain typically occurs several months after treatment and may last several more months.

Changes in Pulmonary Function Tests (e.g., forced expiratory volume (FEV1) decreased; carbon monoxide diffusion capacity (DLCO) decreased; vital capacity abnormal)

Patients enrolled to this study may have some degree of impaired pulmonary function as measured by pulmonary function tests (PFTs), including Forced Expiratory Volume in 1 second (FEV₁), Forced Vital Capacity (FVC), and Diffusing Capacity for Carbon Monoxide (DLCO). The CTCAE Version 4 grading criteria for PFTs assume that all patients have normal baseline pulmonary function. This assumption is not appropriate for this protocol, which is enrolling patients with abnormal baseline function. In order to monitor changes in lung function from baseline, a protocol-specific toxicity classification for PFTs has been developed for use with this study. PFTs will be coded for all patients in both treatment groups using this scale. See RTOG Pulmonary Function Test Toxicity Scale (Section 8.4) for more information.

Other Grade 3 or Higher Adverse Events

All other adverse events Grade 3 or higher, or requiring suspension of therapy, will be reported.

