8.1 Routine Adverse Event Reporting

All expected or unexpected adverse events, regardless of grade or treatment attribution, must be recorded on AE case report forms (CRFs).

Some serious adverse events may require expedited reporting using the AdEERS reporting system, as defined below. **NOTE: All AEs including those submitted to NCI via the Adverse Event Expedited Reporting System (AdEERS) must be recorded on the AE CRF.** Expedited reporting is in addition to and does not supplant the reporting of AEs as part of the data submission requirements for the study.

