10.1.2 Secondary Endpoints

The secondary objective of this Phase III trial is to compare the time-to-locoregional recurrence using a standardized definition of locoregional recurrence to be applied to both arms. In brief, locoregional

recurrence will be defined as recurrence within the same lobe or hilum (N1 nodes), or within 2 cm of the staple line or within 2 cm of the PTV after treatment effects such as scarring have subsided. This will be a first attempt to set comparable locoregional recurrence definitions for these two different treatment modalities.

Other secondary endpoints are adverse events, disease-free survival, and pulmonary function. Adverse event rates will be compared at specific timepoints (1, 3, and 12 months post therapy). Disease-free survival is defined as the time from randomization until documented disease-recurrence or death, whichever occurs first. Patient who are disease-free and alive at the time of analysis will be censored at the time of their last follow-up. Patients will be followed for disease-free survival for a minimum of 5 years. Pulmonary function will be evaluated by PFTs and will be compared at specific timepoints as well as over the entire period of observation.

A tertiary aim of the study is to compare the adverse event rates and PFT values in each arm for patients with low or high Charlson comorbidity index scores, including a test interaction between Charlson Comorbidity Index scores (low vs. high) and treatment arm. If there a substantial interaction term, this index may potentially be used to select patients for SBRT or SR.

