10.3.3 Secondary Endpoint Analyses

Local-regional recurrence-free survival and disease-free survival will be compared using a one-sided logrank test. As for the primary analysis, we will exclude patients who are randomized but then cancel and refuse the treatment to which they were assigned. We will also perform the fully intention to treat approach as a sensitivity analysis.

Analysis of the adverse event rates and PFT values will involve chi-square tests and t-tests and Wilcoxon procedures at each time point as well as a repeated measures analysis of variance (ANOVA) and general estimation equations (GEE) modeling using data from all timepoints. [126] Models will include covariates of patient characteristics as well as treatment arm to perform a conditional analysis of treatment comparison in the presence of potentially confounding variables. The extent of missing data will be explored for non-random influences. [127] Sensitivity analysis will be performed using various simple imputation techniques to ensure results are not unduly influenced by the presence of missing data. [128,129] We examine the impact of imputing using such methods as last-value-carried forward, nearest-neighbor imputation, zero-value imputation, minimum-value imputation, and maximum-value imputation on the result original analysis. The degree of variability in the results will allow for a calibration of the impact of the best and worst case scenarios in terms of patterns in the missing data on the stability of the analytical results.

A tertiary analysis is planned that will compare the adverse events and PFTs profiles in each arm for patients with low or high Charlson Comorbidity Index scores, including a test interaction between Charlson Comorbidity Index scores (low vs. high) and treatment arm. Again, we will use appropriate modeling techniques. Modeling techniques will also be used to determine other prognostic variables that might be used to determine other characteristics that are associated with outcome in the different treatment arms.

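### Section 10.3.3 gives the scheduled pre-treatment adverse event assessment no stated role, so pre-existing grade 3+ conditions may dilute the SR versus SBRT safety contrast

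*Combined protocol and SAP*

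**What the plan says.** The safety objective in Section 1.3.2 is "To compare grade 3 or higher specific adverse event profiles between study arms", at 1, 3, 6 and 12 months. Section 10.1.2 has a shorter list: "Adverse event rates will be compared at specific timepoints (1, 3, and 12 months post therapy". Neither list includes the pre-treatment assessment.

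Section 10.3.3 sets the method: "Analysis of the adverse event rates and PFT values will involve chi-square tests and t-tests and Wilcoxon procedures at each time point". The sentence goes on to repeated-measures ANOVA and GEE over all time points, and the next adds: "Models will include covariates of patient characteristics as well as treatment arm". The characteristics are not listed. The section does not define a treatment-emergent or worsened-from-baseline event, and it does not use attribution.

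In the Study Calendar (Section 3), the row "Adverse event assessment" has its first mark in the column after registration and before SBRT or surgery. Further marks follow at 4 weeks and at 3, 6, 9 and 12 months.

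Section 8.1 sets the recording rule: "All expected or unexpected adverse events, regardless of grade or treatment attribution, must be recorded on AE case report forms (CRFs". It has no rule on conditions present before treatment.

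Section 2.1 admits patients on one major criterion (FEV1 or DLCO at or below 50% predicted) or two minor ones. The eight minor criteria include a score of 3 or more on the "Modified Medical Research Council (MMRC) Dyspnea Scale" and pO2 of 55 mm Hg or less or SpO2 of 88% or less, at rest or on exercise.

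For pulmonary function tests only, Section 5.3.7 rejects the normal-baseline assumption behind CTCAE grading: "This assumption is not appropriate for this protocol, which is enrolling patients with abnormal baseline function". Section 8.4 then grades PFT decline in both arms against the patient's own baseline.

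**The concern.** The protocol accepts that absolute grades mislead when lung function is abnormal at entry, and corrects for this in PFTs. Dyspnea, hypoxia and the remaining terms stay on absolute CTCAE grades. Dyspnea is an expected AE in both arms (Sections 8.3.1 and 8.3.4), and hypoxia was among the common grade 3+ events in Z4032 (Section 8.3.3). What brings some patients into the trial therefore overlaps with what is counted afterwards. A patient with a grade 3 condition before treatment and the same grade after it could count as an event, depending on how the site fills in the form.

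The comparison carries weight beyond its secondary rank. Section 10.1.1 justifies a loss of up to 10 points in three-year survival by an expected fall in grade 3+ events, potentially by half or more. This analysis is where that expectation is tested. The Charlson-by-arm analysis of AEs, which Section 10.1.2 says might help to select patients for one treatment, uses the same counts.

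**Working it through.** The plan states no power, alpha or sidedness for the AE comparison, so there is no design figure to reproduce. What follows is illustration.

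**Inputs from the documents**
- Z4032 30-day grade 3+ events, regardless of attribution (Section 1.1): 29/114 = 25.4% for SR, 33/109 = 30.3% for SR plus brachytherapy. Both percentages reproduce. Pooled: (29 + 33)/(114 + 109) = 62/223 = 27.8%.
- SBRT at half the SR rate, the possibility raised in Section 10.1.1: 27.8%/2 = 13.9%.
- 200 eligible patients per arm (Section 10.2).

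**Assumptions**
- Two-sided 5% test of two proportions, normal approximation.
- A share b of patients in each arm has a pre-existing grade 3+ condition that is recorded again after treatment, independently of new events. The documents give no value for b; 0 to 20% is an assumed range.

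**Formulas**
- Observed rate: p' = 1 − (1 − p)(1 − b).
- Observed difference: p1' − p2' = (1 − b)(p1 − p2). Background shrinks the difference by the factor 1 − b. If p1 = p2 the difference stays zero.
- Power = Φ[(d − 1.96·SE0)/SE1], where d is the observed difference, SE0 uses the pooled rate and SE1 the separate rates.

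**Worked line, b = 10%**
- SR: 1 − 0.722 × 0.90 = 0.350. SBRT: 1 − 0.861 × 0.90 = 0.225. d = 0.125; ratio 0.225/0.350 = 0.64.
- Pooled rate 0.288; SE0 = √(2 × 0.288 × 0.712/200) = 0.0453; SE1 = √(0.350 × 0.650/200 + 0.225 × 0.775/200) = 0.0448.
- (0.1251 − 1.96 × 0.0453)/0.0448 = 0.81, so power is 79%.

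| Assumed b | SR | SBRT | Difference (points) | Risk ratio | Power |
|---|---|---|---|---|---|
| 0 | 27.8% | 13.9% | 13.9 | 0.50 | 93% |
| 2% | 29.2% | 15.6% | 13.6 | 0.53 | 91% |
| 5% | 31.4% | 18.2% | 13.2 | 0.58 | 87% |
| 10% | 35.0% | 22.5% | 12.5 | 0.64 | 79% |
| 20% | 42.2% | 31.1% | 11.1 | 0.74 | 64% |

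**Other anchors**
- SR alone, 25.4% versus 12.7%: power 90%, 87%, 82%, 73% and 57% at the same five values of b.
- SBRT at 16%, the grade 3 and 4 rate given for RTOG 0236 in Section 1.1, against 25.4%: 65% at b = 0, 47% at 10%, 35% at 20%.

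**If the Z4032 rate already contains background**
Suppose 27.8% includes b = 10%. The rate net of background is 1 − 0.722/0.90 = 19.8%, and half of that is 9.9%. The planned analysis would then see 27.8% versus 1 − 0.901 × 0.90 = 18.9%: ratio 0.68, power 56%. Counting only new or worsened events gives 19.8% versus 9.9% and power 80%.

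**The case against.** Several stronger readings are tempting, and the documents support none of them.

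- *Chronic conditions are counted as toxicity.* This would be an inference from silence. Section 8.1 governs recording, not analysis, and nothing tells sites to enter an unchanged condition again after treatment. Section 8 also requires an attribution for every AE, which could separate background from toxicity, although Section 10.3.3 does not say it will be used. If sites already leave unchanged conditions off the follow-up forms, the loss is close to zero.
- *The analysis ignores baseline altogether.* The ANOVA and GEE use all time points and unspecified patient characteristics, so they may include the pre-treatment assessment. Only the per-time-point tests are clearly without a baseline reference.
- *Eligibility selects for severe dyspnea and hypoxia.* It permits them. One major PFT criterion is enough, and PFT change is already graded against baseline. Dyspnea and hypoxia are two of eight minor criteria, two of which are needed, and hypoxia may be on exercise only. Patients are ECOG 0 to 2. The CTCAE thresholds for these terms are not in the documents, so an MMRC score of 3 cannot be equated with CTCAE grade 3.
- *The comparison is biased towards one arm.* Background that is equal under randomisation attenuates the contrast and does not invent a difference.

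The size is also open to challenge. The Z4032 rates are regardless of attribution, so adding b to them may double count; they cover 30 days, whereas the comparisons run to 12 months. The objective concerns specific AE profiles, and acute terms such as surgical hemorrhage would carry little chronic background. The AE comparison does not enter the non-inferiority rule in Section 10.3.1.

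These points stand as limits on size. They do not supply the missing definition, and the last calculation above shows that re-anchoring the Z4032 rate does not by itself make the loss smaller.

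**Conclusion.** The point holds as a gap in specification. A pre-treatment AE assessment is scheduled, the analysis text assigns it no role, and the baseline correction that the protocol adopts for PFTs is not extended to other terms. The possible consequence is attenuation and lost power in the comparison that supports the survival margin, with no false difference between arms.

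The size cannot be fixed from the documents. In the illustration the loss is about 2 percentage points of power at 2% background, 14 at 10% and 29 at 20%. It rests on the assumed b, an equal and independent background in both arms, one pooled grade 3+ proportion, and a two-sided 5% test. For the Charlson analysis, a background that differed between the low and high groups would attenuate the ratio unequally (0.58 at b = 5% but 0.74 at 20% for the same treatment effect). Whether it does differ, the documents do not say.

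**What to change.** In Section 10.3.3, state that the main grade 3+ AE comparison, by arm and by Charlson group, counts events that are new or higher in grade than the same patient's grade for that term at the pre-treatment assessment. Include baseline grade in the GEE. Report all grade 3+ events regardless of baseline alongside, as a sensitivity analysis.

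The cost is analysis-plan wording and modest programming on data already scheduled; no visit or treatment rule changes. There are two small downsides. A pre-existing grade 3 condition that persists unchanged leaves the main count, though it stays visible in the all-events analysis. The baseline grade is also recorded after randomisation, when patient and site know whether surgery or radiation will follow, so its grading could differ by arm. Tabulate baseline grades by arm and keep the all-events analysis as the check on this.

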It is anticipated that the results of Z4032, comparing the local recurrence free survival (LRFS) rates of SR versus SR plus brachytherapy, will be mature in 12/2011. If it appears one arm of Z4032 is superior to the other arm, the present trial will be amended to mandate that the superior SR treatment be used in the SR arm of the trial. At that time, we may also adjust the sample size if the three year overall survival (OS) rate for the SR arm appears to differ considerably from 80%. If neither arm of Z4032 is declared superior, we will continue to allow the choice of including brachytherapy or not as part of the treatment on the SR arm for this trial.

Although the outcome data for Z4032 are not yet mature, there is information available regarding 30-day adverse events and mortality rates for the two treatment arms. The table below summarizes the 30-day adverse event (regardless of attribution) and mortality rates by arm, i.e. the SR and the SR plus brachytherapy arms. The table indicates the number of patients (and percent) that had at least one adverse event of the indicated grade range within 30 days from surgery.

	S N =	SR = 114	SR + brac N =	chytherapy = 109
Adverse event grade	Ν	%	Ν	%
Grade 3+	29	25.4	33	30.3
Grade 4+	8	7.0	8	7.3
Grade 5	1	0.9	2	1.8

The 30-day adverse event and mortality (i.e. Grade 5 adverse event) rates are similar between the two treatment arms.

Sublobar Resection Studies

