10.1.1 Primary Endpoint

The primary aim of this Phase III trial is to test the hypothesis that SBRT for operable high-risk patients with stage I NSCLC is not inferior to SR with or without brachytherapy. The primary endpoint is overall survival defined as the time from randomization until death from any cause. All patients will be followed for the primary endpoint for a minimum of 5 years.

Based on historical data, we expect the three-year survival rate for SR (control group) to be 80%. We will accept a 10% decrement from the three-year survival rate for SR arm of the study to be considered noninferior. Rationale for the up to 10% decrement in three-year survival for the SBRT arm is that SBRT is expected to be significantly better tolerated (i.e. have a significantly better adverse event profile) than SR. One line of evidence to support this expectation is that it has been established that stage I patients who are medically inoperable (unable to tolerate any form of lung resection) can tolerate SBRT because it is less invasive and has a lower adverse event profile compared to SR. Hence, in this high-risk population (patient who can tolerate SR but not the first line surgery of lobar resection), SBRT will likely have a considerably better adverse event profile (and QOL profile) than SR. There is also some evidence in the literature that supports a significantly improved adverse event profile of SBRT compared to SR in this population. Specifically, a large study of 182 patients undergoing segmental resection demonstrated complications in 32.4% of patients [103]. This compares to a recent report of SBRT that reported a 10% rate of grade 3+ toxicities [19]. It is difficult to compare these values because they did not use the same adverse event grading scale. However, this potentially indicates that the expected grade 3+ adverse event rate for SRBT might be half that for SR. Given this, it is felt that an inferiority margin of at most 10% in three year survival is balanced by a anticipated decrease in grade 3+ adverse events of a substantial amount (potentially 50% or more) in SBRT compared to SR.

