10.2 Sample Size

This is a non-inferiority trial designed to determine whether the overall survival rate for SBRT is clinically (and statistically significantly) no worse than the overall survival for SR. We used published survival rates from the literature for SR in this patient population [2, 8, 19, 103]. The 3-year survival rate for SR (control group) appears to be approximately 80%. We will deem SBRT as non-inferior to SR if the 3 year overall survival rate for SBRT is no more than 0.10 less than that for SR. In other words, if the survival rate for SBRT at 3 years is more than 0.10 less than that for SR. In other words, if the survival rate for SBRT at 3 years is more than 0.10 less than the 3 year survival rate for SR, we will declare SBRT to be an inferior treatment compared to SR in terms of overall survival. To power the study, we assumed an exponential distribution for the survival rate and a HR of 1.60 (which reflects a 10% 3-year survival rate for SR is at least 0.10 greater than that for SBRT (0.80 for SR versus 0.70, or less, for SBRT). The alternative hypothesis is that the HR is 1.00 or that the 3 year survival rate for SR compared to SBRT is no more than 0.10. If we reject the null hypothesis, we will assume the two treatments are equivalent with respect to overall survival, if we do not reject the null hypothesis, we will assume that SR is superior to SBRT is no more than 0.10.

To determine the sample size for the trial we assumed a significance level of 0.05, an HR of 1.60 (SBRT versus SR, for the null hypothesis) and set power to be 90%. We plan a single interim analysis when half of the expected events (deaths) have occurred; this will be for futility only. Assuming a 3-year survival rate of 0.80, a HR of 1.60 yields a 3-year survival rate for SBRT of 0.70 or less for the null hypothesis. Assuming an accrual rate of 10 patients per month, an expected accrual duration of 40 months (3 1/3 years), and a minimum follow-up of 42 months (3.5 years), the necessary sample size is 400 eligible patients (200 per arm). To ensure that there is an adequate number of eligible patients (including patient refusals after randomization and prior to treatment), we will have a target accrual that is approximately 5% greater than this or 420 patients. This trial is expected to accrue in approximately 40 months and the final analysis will occur after 166 deaths have been observed or about 82 months (6.8 years) after the first patient is enrolled.

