and sensitivity analysis in the form of Q-TWiST plots set out by Sloan[14]. The secondary endpoint of time until recurrence will be analyzed in the same fashion as the primary endpoint.

Goals 2-4 will attempt to integrate the PRO and survival endpoints into a combined analysis. The primary endpoint for this aspect of the study will be the QALY estimate formed by the combination of the time to recurrence data and the PRO health status assessments of the EQ-5D. Sloan described the detailed process of constructing QALYS and the related analysis that will be used in this protocol [1]. The comparison of the average QALY for time to recurrence will be carried out via the appropriate simulation studies per Cole [13] and sensitivity analysis in the form of Q-TWiST plots set out by Sloan [14]. Further, a new method will be applied to calibrate QALY scores to facilitate their interpretation developed by the ACOSOG statistical group which was presented at ASCO in June 2010 [17]. The secondary endpoint of time until death will be analyzed in the same fashion as the primary endpoint.

The secondary endpoints related to the LCSS and UCSD items and PRO domains of overall QOL, fatigue and anxiety will be compared across treatment arms by creating a pro-rated area under the curve statistic for each patient for each domain measured and using a two-sample t-test.

The impact of baseline (pre-operative) deficits in PRO domains for the LCSS and UCSD items and three single-item PRO domains (overall QOL, fatigue, anxiety) on the two time-related endpoints (time to recurrence and time to death) by incorporating these variables as covariates in the Cox model analyses specified in the main body of the concept.

Missing data are always a consideration on PRO-related studies. Our statistical group has extensive experience and has developed numerous standardized algorithms for dealing with missing data [18]. These algorithms described by Sloan et al [19], involve sensitivity analysis to test for nonrandom influences that might be producing the missing data and the use of alternative imputation methods to ensure that the results of the treatment comparison are robust relative to the presence of the missing data.

References

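### The zero-, minimum- and maximum-value fills planned for missing adverse event and PFT data have no stated arm direction and, read naturally, do not bound the treatment difference

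*Combined protocol and SAP*

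**What the plan says.** Section 10.3.3 describes the secondary comparisons: "Analysis of the adverse event rates and PFT values will involve chi-square tests and t-tests and Wilcoxon procedures at each time point", followed by repeated-measures and GEE models. It says missingness will be examined for non-random patterns, and then: "Sensitivity analysis will be performed using various simple imputation techniques to ensure results are not unduly influenced by the presence of missing data". The methods offered as examples are "last-value-carried forward, nearest-neighbor imputation, zero-value imputation, minimum-value imputation, and maximum-value imputation". The spread of results over these methods, it says, "will allow for a calibration of the impact of the best and worst case scenarios in terms of patterns in the missing data".

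Nothing states whether a fill may differ by arm. Nor is it stated whether minimum and maximum mean the limit of the scale, the sample extreme or each patient's own extreme. The missing-data paragraph for patient-reported outcomes in Section 14.1 provides for "the use of alternative imputation methods to ensure that the results of the treatment comparison are robust relative to the presence of the missing data", but it too names no scenario in which the two arms are filled in opposite directions.

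**The concern.** A best or worst case for a comparison is the arm difference that is most or least favourable to one treatment. It arises when missing patients in one arm did well and those in the other did badly. Filling both arms with a low value, then both with a high value, moves the two arm means together and leaves their difference largely where it was. A reader could take the resulting agreement as robustness when the fills were never able to show the opposite.

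The adverse event comparison carries weight here. Section 10.1.1 justifies the 10-point survival margin by an expected adverse event advantage for SBRT, and Section 10.3.2 says the adverse event profile and quality of life may help decide the preferred treatment. Informative missingness is also plausible. After relapse, the Study Calendar notes and Section 6.2 mention follow-up for survival and quality of life only, so adverse event and PFT assessment may stop then. Section 1.1 expects local recurrence to differ between the arms.

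**Working it through.** The plan gives no figure for missing adverse event or PFT data, so there is nothing of its own to reproduce.

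**Inputs**
- SR grade 3+ rate: 29/114 = 25.4%, from the 30-day Z4032 table in Section 1.1 (SR arm, row "Grade 3+ 29 25.4 33 30.3").
- SBRT grade 3+ rate: 10%, from Section 10.1.1 ("This compares to a recent report of SBRT that reported a 10% rate of grade 3+ toxicities"). The two rates come from different studies and time windows, so they serve as illustration only.
- 200 patients per arm (Section 10.2).
- Missing fractions m1 (SR) and m2 (SBRT): assumed, 5% to 30%. The nearest figure in the documents concerns something else: Section 14.2 expects follow-up blood samples from 80 to 100% of patients.

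**Algebra.** Let p1 and p2 be the observed means (SR, SBRT), and let the outcome run from L to U. With one fill value c in both arms, the SBRT-minus-SR difference is

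(1 - m2)p2 - (1 - m1)p1 + c(m2 - m1).

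Moving c from L to U changes this by (m2 - m1)(U - L). With opposite extremes in the two arms, the interval has width (m1 + m2)(U - L). If m1 = m2 = m, every common fill gives (1 - m)(p2 - p1).

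**Worked case, 20% missing in each arm.** Observed events contribute 0.8 x 0.25439 = 0.20351 (SR) and 0.8 x 0.10 = 0.08 (SBRT).
- Minimum (or zero) in both arms: 0.08 - 0.20351 = -0.1235.
- Maximum in both arms: 0.28 - 0.40351 = -0.1235.
- SR all events, SBRT none: 0.08 - 0.40351 = -0.3235.
- SR none, SBRT all events: 0.28 - 0.20351 = +0.0765.

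**Results** (percentage points, SBRT minus SR; observed difference -15.4):

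| Missing SR / SBRT | Minimum or zero fill | Maximum fill | Arm-opposed bounds |
|---|---|---|---|
| 5% / 5% | -14.7 | -14.7 | -19.7 to -9.7 |
| 10% / 10% | -13.9 | -13.9 | -23.9 to -3.9 |
| 20% / 20% | -12.4 | -12.4 | -32.4 to +7.6 |
| 30% / 30% | -10.8 | -10.8 | -40.8 to +19.2 |
| 10% / 20% | -14.9 | -4.9 | -24.9 to +5.1 |
| 20% / 10% | -11.4 | -21.4 | -31.4 to -1.4 |

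At 10%/20%, the planned fills span 10 points against an attainable 30.

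**Tests** (pooled two-proportion z-test, two-sided). At 20% missing per arm, p = 0.0004 for the minimum fill and 0.009 for the maximum fill. At the bound least favourable to SBRT, p = 0.014 with 5% missing per arm and p = 0.34 with 10%.

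**When the sign can reverse.** With equal missingness, reversal requires m > (1 - m) x 0.154, that is m > 0.154/1.154, or about 13% in each arm. Every missing SBRT patient would need to have had an event and no missing SR patient to have had one.

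**PFT illustration** (all values assumed: mean fraction of baseline 0.85 SR and 0.92 SBRT, range 0.40 to 1.20). With 20% missing per arm, the zero, minimum and maximum fills all give 0.8 x 0.07 = +0.056. Arm-opposed fills within the range give 0.056 ± 0.2 x 0.80, or -0.104 to +0.216. With 20% missing in SR and 10% in SBRT, a zero fill gives 0.9 x 0.92 - 0.8 x 0.85 = +0.148. That is about double the observed 0.07, only because SR has more missing values.

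**The case against.** The strongest reply is that the same-value reading is inferred. The text does not say both arms receive one value, the list is open-ended, and the methods papers it cites are not available here. That stands as a limit on the claim. But no arm-opposed scenario is named, and last-value and nearest-neighbour fills are not extremes. If minimum and maximum mean each patient's own values, the simple shrinkage formula no longer applies, but the fills still push both arms the same way and do not bound the difference.

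A second reply is that the fills do show some variability. This is also correct. They agree exactly only on the point difference and only when missingness is equal; p-values move, and unequal missingness produces a spread. The defect is that the spread is too narrow to be a best-to-worst range, not that it is always zero.

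Third, zero is not always an improper fill. For an adverse event it means no event, and for a change from baseline it means no change. The objection to zero applies to raw FEV1, FVC or DLCO values, where no living patient scores zero.

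Fourth, arm-opposed bounds are deliberately extreme, and at low missingness they do not overturn the comparison. That stands, and it is why a tipping-point analysis is more informative than the bounds alone.

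**Conclusion.** The concern holds in limited form. As written, the fills do not deliver the best-and-worst-case calibration that Section 10.3.3 attributes to them, because no arm direction is given and same-direction fills cannot bound a difference between arms. Whether this would matter depends on missingness that the documents do not report. On the illustrative rates, 5% missing per arm leaves SBRT ahead even at the bound. At 10% the sign holds, but significance would be lost at the extreme. Above about 13% the sign could reverse.

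A reader might infer three stronger things that the documents do not support:
- **That the plan takes a small spread as proof that missing data are harmless.** It speaks only of calibration, presumes no small spread, and also plans to look for non-random missingness.
- **That the non-inferiority conclusion is at risk.** The point concerns the adverse event and PFT secondary endpoints; the overall survival analysis does not use these fills.
- **That PFT values underpin the survival margin.** Section 10.1.1 rests it on the adverse event profile, with quality of life in parentheses. PFT decline enters only in so far as Section 8.4 grades it as toxicity.

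This is a cheap improvement, of low to moderate severity.

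**What to change.** In Section 10.3.3:
- **Adverse events:** add two arm-opposed scenarios (missing SBRT patients worst with missing SR patients best, and the reverse). Add a tipping-point table showing which combinations of event rates among missing patients in each arm would change the conclusion.
- **PFTs:** add an arm-specific delta-shift analysis, increasing the shift until the conclusion changes.
- **Zero fill:** do not use it for raw FEV1, FVC or DLCO values.
- **Wording:** state the fill value and its direction by arm for every method kept, and stop describing same-direction fills as best and worst cases.

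The simple fills can otherwise stay as supplementary checks; the defect does not require replacing them all or mandating multiple imputation. The cost is SAP wording and modest programming, with no new data. The drawback is that the reported uncertainty will look larger.
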